1. INTRODUCTION

1.1. Background

Naked Biome hypothesizes that eliminating resident disease-associated bacterial strains and replacing them with a health-associated *Propionibacterium acnes* (*P. acnes*) transplant may help to improve, mitigate, treat, or prevent acne flares. In a Phase I single application study of NB01 conducted by the Sponsor, all 10 subjects completed the study without any drug-related adverse events (AEs).

Genotypic and phenotypic work performed by the Sponsor has identified candidate strains sourced from healthy subjects that match all our criteria for health as defined by the literature. Genotypically, the Sponsor's candidate strain is a *P. acnes* ribotype 2, deoR+ (Johnson et al. 2016), lipase type II+ (Tomida et al. 2013) which contains a complete CRISPR system (Johnson et al. 2016), does not contain the pIMPLE plasmid (Kasimatis et al. 2013), and has no identifiable genomic evidence of antibiotic resistance. Phenotypically, the candidate strain produces low levels of porphyrin, comparable to other healthy associated ribotype 2's in the literature and is sensitive to all five antibiotics tested internally (Clindamycin, Doxycycline, Erythromycin, Minocycline, Tetracycline as was measured with Etest [bioMérieux]).

Additional safety assessments were performed by CHR-Hansen, Naked Biome's GMP manufacturer, who confirmed that no genomic antibiotic resistance genes were present and that the candidate strain was sensitive to 13 out of 14 tested antibiotics, resistant only to metronidazole which *P. acnes* has known natural resistance to and was additionally non-hemolytic and non-cytotoxic.

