7. ADVERSE EVENT REPORTING AND TOXICITY MANAGEMENT

7.1. Adverse Event Definitions

An AE is any untoward medical occurrence associated with the use of a drug in humans, whether or not considered drug related.

An AE (also referred to as an adverse experience) can therefore be any unfavorable and unintended sign (e.g., an abnormal laboratory finding), symptom, or disease temporally associated with the use of a drug, without any judgment about causality. An AE can arise from any use of the drug (e.g., off-label use, use in combination with any drug) and from any route of administration, formulation, or dose, including an overdose.

A **suspected adverse reaction** is any AE for which there is a reasonable possibility that the drug caused the event. “Reasonable possibility” means there is evidence to suggest a causal relationship between the drug and the AE.

An **adverse reaction** is any AE caused by a drug. Adverse reactions are a subset of all suspected adverse reactions for which there is reason to conclude that the drug caused the event. A suspected adverse reaction implies a lesser degree of certainty about causality than adverse reaction, which means any AE caused by a drug. For the purposes of prescription drug labeling, the term adverse reaction means an undesirable effect, reasonably associated with the use of a drug that may occur as part of its pharmacological action or may be unpredictable in its occurrence.

An AE does not include the following:

Medical or surgical procedures such as surgery, endoscopy, tooth extraction, and transfusion. The condition that led to the procedure may be an AE and must be reported.

Pre-existing diseases, conditions, or laboratory abnormalities present or detected before the screening visit that do not worsen.

Situations where an untoward medical occurrence has not occurred (e.g., hospitalization for elective surgery, social and/or convenience admissions).

Overdose without clinical sequelae.

Any medical condition or clinically significant laboratory abnormality with an onset date before the consent form is signed and not related to a protocol-associated procedure is not an AE. It is considered to be pre-existing and should be documented on the medical history CRF.

An AE or suspected adverse reaction is considered “unexpected” if it is not listed in the IB or is not listed at the specificity or severity that has been observed; or, if an IB is not required or

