Moderate - The AE is usually alleviated with additional specific therapeutic intervention. The event interferes with usual activities of daily living, causing discomfort, but poses no significant or permanent risk of harm to the research participant.

Severe - The AE interrupts usual activities of daily living or significantly affects clinical status or may require intensive therapeutic intervention.

The PI must determine the relationship of the AE to the study drug according to the following categories:

Definitely related - An event that follows a reasonable temporal sequence from administration of the study drug; that follows a known or expected response pattern to the study drug; and that is confirmed by improvement on stopping or reducing the dosage, and reappearance of the event on repeated exposure (re-challenge).

Probably related - An event that follows a reasonable temporal sequence from administration of the study drug; that follows a known or expected response pattern to the study drug; and that is confirmed by improvement on stopping or reducing the dosage of the study drug; and that is unlikely to have been caused by concurrent/underlying illness or other drugs, procedures, or other causes.

Possibly related - An event that follows a reasonable temporal sequence from administration of the study drug; that follows a known or expected response pattern to the study drug; but may have been caused by concurrent/underlying illness, other drug, procedure, or other causes.

Unlikely related - An event that does not follow a reasonable temporal sequence from administration of the study drug; that does not follow a known or expected response pattern to the study drug, or most likely was caused by concurrent/underlying illness, other drug, procedure, or other causes, because of their known effects.

Not Related - An event almost certainly caused by concurrent/underlying illness, other drug, procedure, or other causes.

The PI should categorize the outcome of the AE according to the following categories:

Fatal - Termination of life as a result of an AE.

Not Recovered/Not Resolved - AE has not improved or the subject has not recuperated.

Recovered/Resolved - AE has improved or the subject has recuperated.

Recovered/Resolved with Sequelae - subject recuperated but retained the pathological conditions resulting from the prior disease or injury.

Recovering/Resolving - AE is improving or the subject is recuperating.

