If an SAE occurs during the study and is determined by the Sponsor to be at least possibly related to the study drug, enrollment of new subjects and dosing of active subjects will be halted. A safety review will occur using an independent medical reviewer who will have access to the subject's treatment allocation. This review shall be completed promptly within 5 business days. The independent medical reviewer will provide a written recommendation to the Sponsor to continue the study, discontinue the study or modify the study protocol. The Sponsor is responsible for promptly reviewing the independent medical reviewer's recommendations, accepting or rejecting these recommendations, and determining whether amendments to the protocol or changes in study conduct will be required. The Sponsor will provide the final written decision regarding the study status. A summary of the event should also be reported to FDA as part of an IND Safety Report in accordance with Section 7.2.2. FDA should also be notified within 48 hours of the final decision and provided an IND Safety Follow-up Report as necessary (if new information was collected since the initial Safety Report).

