8.3. Endpoints

8.3.1. Primary Safety Endpoints

- Incidence (severity and causality) of any local and systemic AEs.
- Number of subjects with presence (and severity) of each LSR and each time point.
- Changes from Screening/Baseline in physical examination findings at Visit 5/EOT.
- Changes from Screening/Baseline in vital signs at Visit 5/EOT.
- Changes from Screening in local CBC at Visit 5/EOT.

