10.2. Subject Discontinuation

A subject may be withdrawn from the study prior to completion for any of the following reasons:

- Adverse event
- Death
- Lost to follow-up
- Subject non-compliance
- PI decision
- Pregnancy
- Progressive disease
- Significant protocol deviation
- Study terminated by Sponsor
- Withdrawal of consent by subject*

*If the subject decides to withdraw from the study due to an AE it should be classified as withdrawal due to an AE.

If a subject withdraws prior to the Week 12 visit, every attempt should be made to complete final study procedures prior to discharge from the study. If a subject withdraws prematurely during the treatment period for any reason, the Week 12/EOT procedures will be completed. When a subject is withdrawn from the study for a treatment-related AE (i.e., possibly, probably or definitely related as defined in [Section 7.2](#)), when possible, the subject should be followed until resolution of the AE.

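### The causality scale in Protocol 7.2 does not let a new type of NB01 reaction be scored possibly related or higher, which distorts the causality part of the primary safety endpoint

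*Protocol*

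**What the plan says.** The first primary safety endpoint (Protocol 8.3.1) is "Incidence (severity and causality) of any local and systemic AEs". SAP 8.12.2 tabulates treatment-emergent AEs by system organ class and preferred term, and again by maximum severity and closest relationship across five categories.

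Protocol 7.2 defines those categories, and the investigator must choose one:

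- *Definitely* and *Probably related* both need a reasonable temporal sequence and an event "that follows a known or expected response pattern to the study drug; and that is confirmed by improvement on stopping or reducing the dosage". Definitely adds recurrence on re-exposure. Probably adds that other causes are unlikely.
- *Possibly related* needs a reasonable temporal sequence and an event "that follows a known or expected response pattern to the study drug; but may have been caused by concurrent/underlying illness" or by another cause.
- *Unlikely related* is an event without a reasonable temporal sequence and "that does not follow a known or expected response pattern to the study drug, or most likely was caused by" something else.
- *Not related* needs an almost certain other cause.

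Protocol 7.1 defines a suspected adverse reaction by a reasonable possibility of causation, which "means there is evidence to suggest a causal relationship between the drug and the AE". It says nothing there about a response pattern.

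On earlier exposure, Protocol 1.1 reports that "all 10 subjects completed the study without any drug-related adverse events".

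**The concern.** NB01 is a live bacterial product with very little human exposure, and Protocol 1.2.2 says there are no in vivo animal data. A Phase 1B safety trial of such a product exists largely to find reactions nobody has yet described. The causality scale nevertheless makes resemblance to a described or anticipated reaction a condition of any related score. The events of most interest are the ones it cannot call related.

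At stake is the causality component of the primary endpoint. A new drug effect would be shown as Unlikely, or would be placed ad hoc by each investigator because no category fits. The same event could also carry two verdicts: a reasonable possibility on the written SAE report (Protocol 7.2.2) and Unlikely on the AE form. Some safety provisions also refer to relatedness, so their reach has to be checked one by one.

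**Working it through.** The plan gives no figure for this point and no sample size calculation (Protocol 8.1), so there is nothing to reproduce. The check is a logical enumeration of the scale, followed by a reading of each rule that mentions relatedness.

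**Step 1. Run a new type of reaction through the scale.** Take an event with a reasonable temporal sequence that does not fit the known or anticipated pattern. Vary three things: improvement off drug, recurrence on re-exposure (possible only after improvement), and the strength of another cause at four levels. That gives 3 × 4 = 12 combinations. The result does not depend on improvement or recurrence.

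| Other cause | *Unlikely*: no timing AND no pattern, or other cause most likely | *Unlikely*: any one ground suffices |
|---|---|---|
| None or improbable | no category fits | Unlikely |
| May have caused it | no category fits | Unlikely |
| Most likely | Unlikely | Unlikely |
| Almost certain | Not related | Unlikely and Not related |

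In none of the 12 combinations, under either reading, does the event reach Possibly, Probably or Definitely. Under the first reading, 2 × 3 = 6 of the 12 have no category at all.

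**Step 2. What counts as expected.** Section 7.2 does not define it. Sections 1.1 and 1.4 name photosensitivity, opportunistic infection, irritation, dryness, redness and worsening of acne, and the list in 1.4 is expressly open. Section 7.1, in contrast, treats an effect anticipated only from pharmacology as unexpected if it is not specifically listed for the drug. The affected set therefore ranges from reactions an investigator finds implausible for topical bacteria (broad reading of expected) to nearly everything (narrow reading).

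**Step 3. Compare with 7.1.** Sections 7.1 and 7.2.2 provide for events that are both suspected reactions and unexpected. On the narrow reading of expected, the 7.2 scale cannot score such an event as related.

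**Step 4. Check each rule.**

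| Provision | Criterion used | Affected? |
|---|---|---|
| Causality tabulation (Protocol 8.3.1, SAP 8.12.2) | 7.2 scale | Yes |
| Follow-up after withdrawal (10.2) | "for a treatment-related AE (i.e., possibly, probably or definitely related as defined in" Section 7.2 | Yes; 7.2 still asks that AEs be followed to resolution or stabilization where possible |
| SAE halt (7.2.1) | "determined by the Sponsor to be at least possibly related to the study drug" | Unclear: the Sponsor decides and 7.2 is not cited, but 7.2 is the only place that defines possibly related |
| Final stop at three NB01-related DLTs (7.2.1) | Relatedness, no standard given | Unclear |
| DLT identification, three-DLT halt and review (7.2.1) | No clear other cause; then unblinded allocation | No |
| SAE reporting (7.2.2) | All SAEs, whatever the relationship | No |
| SAE causality statement and IND reports (7.2.2) | Reasonable possibility | No |

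**Step 5. Scale of exposure.** With 36 subjects at 2:1, about 36 × 2/3 = 24 receive NB01 and 12 vehicle. SAP 8.8 gives 77 planned doses and a denominator of 75, so NB01 exposure is about 24 × 75 = 1,800 to 24 × 77 = 1,848 applications. The human experience behind any known pattern is 10 × 1 = 10 applications with no drug-related event.

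**The case against.** The strongest reply is that the safety net does not hang on this scale. A new systemic reaction of Grade 2 or more, or a local one of Grade 3 or more, with no clear other cause is a DLT whatever its 7.2 score. All SAEs are reported, with a separate reasonable-possibility judgement. Every treatment-emergent AE stays in the overall incidence tables, and the vehicle arm gives a blinded comparison. All of this stands. A reader might infer that a new reaction escapes every rule tied to relatedness; Step 4 shows that the documents do not support that.

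A reader might also infer that such an event can only be scored Unlikely. That is one reading of an ambiguous sentence; on the other reading the event has no category. A third tempting inference is that only a short closed list of effects can count as expected. Section 1.4 leaves its list open, and the Investigator's Brochure is not among the documents.

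The appeal to the vehicle arm is weaker. For AEs below DLT grade, individual causality and the arm comparison are the main evidence, and the comparison is thin. If two subjects have a given AE and the drug plays no part, both fall in the NB01 arm with probability (24 × 23)/(36 × 35) = 0.44. For three subjects it is (24 × 23 × 22)/(36 × 35 × 34) = 0.28. Incidence by arm cannot replace a sound causality score.

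**Conclusion.** The point holds in a bounded form. A plausibly timed reaction outside whatever counts as expected cannot be scored possibly related or higher under Protocol 7.2, even with improvement off drug, recurrence on re-exposure and no other cause. This conflicts with the definition in 7.1. It moves the causality part of the primary safety endpoint away from related, or leaves such events unclassifiable.

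One further provision (follow-up in 10.2) is affected directly, with partial cover from 7.2. Two (the SAE halt and the final DLT stop in 7.2.1) may be affected because their standard is not stated. AE counts, DLT identification and the three-DLT halt, SAE reporting and IND reporting are not affected.

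The number of AEs involved cannot be computed: it depends on the undefined term expected and on which events occur. The exposure figures assume the 2:1 allocation of 36 subjects was met exactly. The arm-chance figures also assume that, without a drug effect, affected subjects fall at random among the 36. This should be corrected, but it does not invalidate the trial.

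**What to change.** 1. In Protocol 7.2, drop the response-pattern condition as a requirement of *Possibly related*. Define that category by a reasonable temporal sequence and a reasonable possibility of causation as in 7.1, whether or not another cause could also explain the event.
2. In *Unlikely related*, remove lack of a known pattern as a stand-alone ground, and state whether the remaining grounds are alternatives or joint conditions.
3. In *Probably* and *Definitely related*, make the pattern supportive rather than mandatory. Otherwise a new reaction confirmed by re-exposure would still be capped at Possibly.
4. In Protocol 7.2.1, state which relatedness standard the SAE halt and the final DLT stop use, and reconcile both with 7.1 and 7.2.
5. Protocol 3.3 says the 36 subjects were already randomized. AEs already scored should therefore be re-reviewed on the aligned definitions, under blind, before the statistician is unblinded at the data freeze in SAP 8.3. AEs first reported at the Week 16 call should be scored on the aligned scale from the start. The study report should state the change.

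No new table is needed, because the five categories in SAP 8.12.2 can be collapsed to related versus not related. The cost is an amendment with IRB approval (Protocol 9.2.1), matching eCRF instructions and a short blinded re-review. A few more AEs will be classed as possibly related, in both arms.

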7.2.1. Dose Limiting Toxicity and Stopping Rules

The Medical Monitor will consider DLT when reviewing the safety data and making recommendations for discontinuing a subject from the study per [Section 10.2](#). A DLT is defined as a new onset systemic Grade 2 or higher (CTCAE Version 5.0, [Appendix 4](#)) AE for which there is no clear alternative explanation of the cause of the AE. In the event a subject is enrolled in the study with a baseline medical condition that would not exclude the subject from entering the study, but meets the classification criteria for a systemic Grade 2 (or higher) or non-systemic (local) Grade 3 (or higher) event, a worsening of the baseline condition during the study that results in an increase in one grade above their Baseline grade shall warrant assessment as a potential DLT.

Non-systemic (local) AEs Grade 3 or higher for which there is no clear alternative explanation of the cause of the AE will also be considered DLTs. Any subject who experiences a DLT, as described above, must discontinue treatment and be scheduled for a final visit. Any DLTs that are Grade 2 or greater systemic AEs must be reported by the PI immediately. If three or more subjects experience DLTs in the study, enrollment in the study will be halted, and a safety review will occur using an independent medical reviewer who will have access to the subject's treatment allocation. This review shall be completed promptly within 10 business days. Subjects who are active in the study will be instructed to withhold study drug applications during the safety review period. If all of the subjects experiencing DLTs (i.e. three or more) are found to be subjects receiving the active NB01 study drug, the independent medical reviewer will provide a written recommendation to the Sponsor to continue the study, discontinue the study or modify the study protocol. The Sponsor is responsible for promptly reviewing the independent medical reviewer's recommendations, accepting or rejecting these recommendations, and determining whether amendments to the protocol or changes in study conduct will be required. The Sponsor will provide the final written decision regarding the study status. In the event this is not the case, the independent medical reviewer will notify the Sponsor and Medical Monitor of how many subject's DLTs were in subjects receiving vehicle (e.g. Y subjects). In the event Y new subjects experience DLTs, the independent medical reviewer review process outlined above will be repeated. This process will be repeated throughout the entire study until the study is complete or

the stopping rule has been met. In the event that a total of three (3) or more subjects experience DLTs related to NB01 study drug, the study will be discontinued.

If an SAE occurs during the study and is determined by the Sponsor to be at least possibly related to the study drug, enrollment of new subjects and dosing of active subjects will be halted. A safety review will occur using an independent medical reviewer who will have access to the subject's treatment allocation. This review shall be completed promptly within 5 business days. The independent medical reviewer will provide a written recommendation to the Sponsor to continue the study, discontinue the study or modify the study protocol. The Sponsor is responsible for promptly reviewing the independent medical reviewer's recommendations, accepting or rejecting these recommendations, and determining whether amendments to the protocol or changes in study conduct will be required. The Sponsor will provide the final written decision regarding the study status. A summary of the event should also be reported to FDA as part of an IND Safety Report in accordance with Section 7.2.2. FDA should also be notified within 48 hours of the final decision and provided an IND Safety Follow-up Report as necessary (if new information was collected since the initial Safety Report).

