7.4. Toxicity Management

A dose mitigation strategy will be employed whereby, with Medical Monitor approval, the dose may be reduced/modified according to the individual subject's tolerance. Typical modification may include short drug holiday periods off therapy, every other day dosing, etc. Such changes however shall not be made without the written approval of the Medical Monitor.

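### Section 7.2.1 asks for immediate reporting of systemic DLTs only, although non-serious local Grade 3+ DLTs count equally toward the halt and the stopping rule (low severity, cheap to fix)

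*Protocol*

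**What the plan says.** Protocol Section 7.2.1 first makes a new-onset systemic AE of CTCAE Grade 2 or higher a DLT when no other cause is clear. It then adds a second kind: "Non-systemic (local) AEs Grade 3 or higher for which there is no clear alternative explanation".

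What follows in that section applies to DLTs of either kind:
- The affected subject must stop treatment and be scheduled for a final visit.
- "If three or more subjects experience DLTs in the study, enrollment in the study will be halted".
- An unblinded independent review follows: "This review shall be completed promptly within 10 business days". Meanwhile, "Subjects who are active in the study will be instructed to withhold study drug applications during the safety review period".
- If some of the DLTs (Y of them) were on vehicle, Y new DLTs trigger another review.
- "In the event that a total of three (3) or more subjects experience DLTs related to NB01 study drug, the study will be discontinued".

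The one sentence on when the PI reports a DLT is narrower: "Any DLTs that are Grade 2 or greater systemic AEs must be reported by the PI immediately". It does not say to whom.

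**The concern.** The halt works from a running count of subjects with DLTs. The Synopsis plans about three centers, so no single site can be relied on to know that the third DLT has occurred. Someone central has to be told of each one. The protocol times the review at 10 business days but sets no time for notice of a local DLT that may be the event starting it.

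The subject with the DLT has already stopped. What is at stake is the other active subjects, who go on applying study drug until the trigger is recognised. The repeat-review rule is the most sensitive place: with Y = 1, one late local report delays the next review on its own. Local events are plausible for a product applied daily to the face, and Section 1.4 lists irritation, dryness and redness among the risks.

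**Working it through.** The plan gives no figure to reproduce. The check is whether any text sets a notice time for a non-serious local Grade 3+ DLT.

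| Route | Covers this event? | Time stated |
|---|---|---|
| 7.2.1, DLT reporting sentence | No, systemic only | Immediately |
| 7.2.2, telephone report to the Medical Monitor | Only if serious | Immediately |
| 7.2, AE CRF | Yes | None |
| 9.1.6, eCRF entry | Yes | Timely, with no limit and no alert |
| 7.2.1, Medical Monitor's safety review | Yes, once the data arrive | None |
| 3.3 and 7.4, approval of a dose change | Only if the dose is first paused or reduced | Before the change |
| 10, End of Study form | Yes | None |
| Appendix 2, footnote t, EOT procedures after early discontinuation | Schedules a visit, notifies nobody | As soon as possible |
| SAP 8.12.2 | Tabulates DLTs only | None |

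Two of these need a closer look.

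1. Section 7.2.1 states: "The Medical Monitor will consider DLT when reviewing the safety data and making recommendations for discontinuing a subject from the study". This gives the Medical Monitor a part in discontinuation, but it presupposes that the data have arrived and sets no time for sending them.
2. Section 7.4 states of dose reductions and modifications: "Such changes however shall not be made without the written approval of the Medical Monitor". A site that pauses drug first must therefore contact the Medical Monitor early. But Section 7.2.1 makes discontinuation mandatory after a DLT, so a site that follows it directly has no dose change to seek approval for.

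What remains is a non-serious local DLT of Grade 3 or higher that goes straight to permanent discontinuation.

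**Can the delay be sized?** Excess exposure is roughly the number on drug per day times the lag in days. The documents give neither. The plateau number can be approximated as 36 × 77 / A, where 36 subjects is from Section 3.3, 77 doses from SAP 8.8, and A is the accrual period in days. This assumes even accrual, no dropout and full adherence:
- A = 245 (one year less about 120 days of participation): 2772/245 = 11.3
- A = 180: 2772/180 = 15.4
- A = 120: 2772/120 = 23.1

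The result doubles across assumed accrual periods. Once randomization is complete the true number falls from the plateau to zero over at most 77 days, the lag is unknown, and about a third of applications would be vehicle. No figure obtained this way is a bound, so none is used.

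**The case against.** The best case against the point is that harm needs several things at once. The event must be local, Grade 3 or higher, non-serious and without a clear alternative cause, and it must still be unreported when it is the one that completes the trigger. Each condition removes cases:
- Any systemic DLT among the three is reported immediately.
- The listed skin reactions become AEs only under the conditions in Section 3.1.2: medical intervention, withholding or stopping drug, or spread 2 cm beyond the treatment area.
- The severe category in Section 7.2 overlaps with the seriousness criteria in Section 7.2.2. Either the PI or the Sponsor may call an event serious, and a single SAE that the Sponsor judges at least possibly related halts dosing by itself.
- Giving systemic events priority is understandable for a live bacterium.
- Section 3.3 reports 36 subjects randomized in the past tense. The enrollment halt then has little left to stop, and an amendment could help only during the remaining run-off.
- A Study Reference Manual exists (Sections 5.6 and 7.2.2) and may set notice times.

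All of this stands and lowers the weight of the point. It does not remove it. Priority for systemic events does not explain why an event that counts equally toward stopping has no reporting time, and none of the listed routes supplies one for the residual case.

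A reader might go further and infer that the stopping rule cannot operate, or that local DLTs go unreported. The documents do not support either: local DLTs must be recorded, the subject must stop, and the count can still be made. Only its timing is open. Nor can one say that no time was set anywhere, since the manual was not seen.

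**Conclusion.** The point holds in a narrow form and at low severity. The protocol's immediate-reporting sentence leaves out one of the two kinds of DLT on which the halt, the repeat review and final discontinuation depend, and it names no recipient. Followed as written, it allows recognition of the triggering DLT to be late while other subjects keep dosing. This is more than a missing detail, because a stated rule excludes events that the count needs.

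The size cannot be computed from the documents. A reader might be tempted to quote a maximum number of extra applications per day of delay. That would rest on an assumed accrual pattern and an assumed lag, and would say nothing about how likely three DLTs are. The conclusion rests on the protocol and SAP text alone and assumes that the Study Reference Manual does not already close the gap.

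**What to change.** First check whether the Study Reference Manual already sets a notice time for local DLTs. In either case, bring the protocol into line by replacing the reporting sentence in Section 7.2.1 with: *Any DLT, systemic or local, must be reported by the PI to the Medical Monitor immediately*, by the telephone route that Section 7.2.2 already provides for SAEs. This also supplies the missing recipient. Leave the DLT definitions, the three-subject threshold and the review process as they are.

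The cost is a short amendment with IRB approval before implementation (Section 9.2.1), a memo to sites and a few extra calls. No new reporting system is needed. In this trial the change is useful only while subjects are still applying study drug.
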